6.4. Method of Assigning Subjects to Treatment

Subjects will be centrally assigned to randomized study drug using an Interactive Web Response System (IWRS). Before the study is initiated, the log in information and directions for the IWRS will be provided to each study site.

On Day 1 of the Double-Blind Treatment Period, subjects will be randomly assigned to 1 of 3 treatment groups (etrasimod 2 mg, etrasimod 1 mg, or placebo) in a 3:3:2 ratio. Randomization will be stratified by baseline history of esophageal dilation (yes/no) and ongoing PPI therapy at study entry (yes/no).

At the start of the Extension Treatment Period, subjects who were randomized to either etrasimod 1 mg or 2 mg during the Double-Blind Treatment Period will be assigned to the same treatment as their Double-Blind Treatment Period treatment. Subjects who were randomized to placebo during the Double-Blind Treatment Period will be re-randomized to etrasimod 1 mg or 2 mg (1:1 ratio) for the Extension Treatment Period.

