9.4. Extension Treatment Period

9.4.1. Week 24 Visit

The Week 24 visit will be used to assess eligibility for the Extension Treatment Period and is considered the beginning of the Extension Treatment Period. During this visit, eligibility for

entry into the Extension Treatment Period will be confirmed (ie, meets eligibility criteria; Section 4.3).

At the Week 24 visit, vital signs should be measured first, followed by ECG, predose PK sample collection, study drug dosing at the study site, and first-dose cardiac monitoring (direct observation) for at least 4 hours in all subjects continuing in the Extension Treatment Period. Cardiac monitoring is required because there is a subset of subjects who will transition from placebo in the Double-Blind Treatment Period to an etrasimod dose in the Extension Treatment Period. Refer to Section 10.6.7.4 for detailed guidance on first-dose cardiac monitoring and subject discharge criteria postdose.

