APPENDIX 1: SCHEDULES OF ASSESSMENTS

Table 7: Schedule of Assessments – Screening, Double-Blind Treatment Period, and Safety Follow-Up Period

Evaluation	Screening Period	24-Week Double-Blind Treatment Period									Safety Follow-Up Period	
	D –35 to D –1	W0/D1	W2/ D15 (± 3) [Tele-health]	W4/ D29 (± 3)	W8/ D57 (± 5)	W12/ D85 (± 5) [Tele-health]	W16/ D113/ (± 5)	W20/ D141 (± 5) [Tele-health]	W24/ D169 ^a (± 5)	ET ^b	2-Week F-U Visit (± 3) [Tele-health]	4-Week F-U Visit (± 3)
Informed consent	X											
Inclusion/exclusion criteria	X	X							X			
Demographics, social and family history	X											
Medical history ^c	X	X										
Prior and concomitant therapies	X	X	X	X	X	X	X	X	X	X	X	X
Virology screen (HIV, HBV, HBsAg, HCV)	X											
Randomization/re-randomization		X							X			
eDiary training ^d	X											
eDiary monitoring ^e	X	X	X	X	X	X	X	X	X	X		
Adverse event assessment	X	X	X	X	X	X	X	X	X	X	X	X
Vital signs ^f	X ^f	X ^f		X	X		X		X	X		X
12-lead ECG ^g	X	X							X	X		
Physical examination ^h		X								X		
Pulmonary function test ⁱ	X								X	X		X

Evaluation	Screening Period	24-Week Double-Blind Treatment Period									Safety Follow-Up Period	
	D -35 to D -1	W0/D1	W2/D15 (± 3) [Tele-health]	W4/D29 (± 3)	W8/D57 (± 5)	W12/D85 (± 5) [Tele-health]	W16/D113/ (± 5)	W20/D141 (± 5) [Tele-health]	W24/D169 ^a (± 5)	ET ^b	2-Week F-U Visit (± 3) [Tele-health]	4-Week F-U Visit (± 3)
Ophthalmoscopy with OCT ^j	X								X	X		X
Pregnancy test ^k	X	X		X	X	X	X	X	X	X		X
CCI		■										
TBNK panel	X	X		X	X		X		X	X		X
Laboratory tests ^l	X	X		X	X		X		X	X		X
EGD and biopsies ^m	X						X		X	X		
PK assessments ⁿ		X		X	X		X		X	X		X
CCI		■					■		■			
Study drug dispensation ^p		X			X		X		X ^q			
Study drug accountability ^r			X	X	X	X	X	X	X	X		
In-person study drug dosing ^s		X		X	X		X		X			
Qualitative interview (optional) ^t									X			

^a For subjects who complete Week 24 and are eligible to enter the Extension Treatment Period, the Week 24 visit will be used to assess eligibility for the extension and may also serve as the Day 1 visit of the Extension Treatment Period. Subjects on placebo during the 24-Week Treatment Period will be re-randomized to study drug for the Extension Treatment Period (Section 6.4).

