 - ^g Safety 12-lead ECGs will be performed with the subject in the supine position prior to blood sample collection and after vital signs are measured at Screening and prior to randomization on Week 0/Day 1 (Baseline), and 4 hours (± 15 minutes) after dosing on Week 0/Day 1. At the Week 24 visit, vital signs should be measured first, followed by ECGs, predose PK sample collection, study drug dosing at the study site, and first-dose cardiac monitoring for subjects continuing in the Extension Treatment Period.
 - ^h Complete physical examination (including assessments of the skin, head, eyes, ears, nose, throat, thyroid, lungs, heart, abdomen, back, lymph nodes, extremities, body weight, and height [height collected at Week 0/Day 1 Visit only]) should be performed at Week 0/Day 1 and the ET visit.
 - ⁱ PFTs include FEV₁ and FVC measurements. Where locally available, DLCO measurements will also be performed (sites where DLCO is not available should consult the Sponsor or Sponsor's delegate). If Week 24 or ET result is abnormal, then testing should be repeated as soon as able. Post-screening PFTs may be performed within 7 days of the study visit. Details regarding additional PFTs are provided in Section 10.6.5.
 - ^j Scheduled non-screening ophthalmoscopy with OCT may be performed within 7 days of the study visit. Screening ophthalmoscopy with OCT is to be conducted with subjects' pupils dilated (Section 10.6.6).
 - ^k Only for women of child-bearing potential. Serum β -hCG test required at screening. On Day 1, urine pregnancy test must be performed and negative test result verified prior to dosing. Monthly urine pregnancy test either at home or at the study site at all other visits. Visual inspection of the test result via videoconferencing for virtual assessment is recommended. If at any point there is a positive urine β -hCG test, the subject will have study treatment interrupted and a serum sample submitted to the central laboratory for β -hCG testing (Section 10.6.9).
 - ^l Clinical laboratory tests will include serum chemistry, CBC with differentials, and coagulation. Screening samples should be obtained, and results must be available and reviewed prior to the first dose of study treatment. On other study visits, samples should be obtained prior to the daily dosing. Refer to Section 10.6.4.

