6.2. BASELINE

Unless otherwise specified, Baseline for the Double-Blind Treatment Period is defined as the last non-missing measurement taken prior to the first dose (including unscheduled assessments), and Baseline for the Extension Treatment Period is defined as the last non-missing measurement taken prior to the date of first dose in Extension Treatment Period at Week 24. If measurements include time (except for Quality of Life assessments (QoL)), the date/time will be used to define Baseline. Otherwise, only dates will be compared. QoL baseline is measured on Day 1 prior to the first dose. In the case where the last non-missing measurement and the date of first dose coincide and time is not collected, if the measurement was planned in the protocol to be done prior to the date of first dose, that measurement will be considered in defining Baseline.

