6.4. WINDOWING CONVENTIONS

All scheduled study visits are defined relative to Study Day 1, the date of first dose. Scheduled visit windows are defined in Appendix 1 of the protocol. A windowing convention will be used to determine the analysis visit value for a given measurement and will be applicable for all by-visit summaries and analyses for efficacy and safety data. See Table 3 below for specific visit windows.

Visit Windows for Efficacy and Safety Analyses

For all efficacy (except for DSQ total score), CCI health-related quality of life, safety labs and vital signs.	
Scheduled Study Visit (Protocol Scheduled Day)	Analysis Visit Window (Study Day)
Baseline (Double-Blind Treatment Period)	≤ 1 , in addition to Study Day ≤ 1 , a measurement also needs to fulfill the baseline criteria identified in Section 6.2 in order to be considered as baseline measurement
Week 0 (Day 1)	1
Week 2 (Day 15 \pm 3)	2 to 22
Week 4 (Day 29 \pm 3)	23 to 43
Week 8 (Day 57 \pm 5)	44 to 71
Week 12 (Day 85 \pm 5)	72 to 99
Week 16 (Day 113 \pm 5)	100 to 127
Week 20 (Day 141 \pm 5)	128 to 155
Week 24 (Day 169 \pm 5)	156 to 183
Week 28 (Day 197 \pm 7)	184 to 211
Week 32 (Day 225 \pm 7)	212 to 274
Week 46 (Day 323 \pm 7)	275 to 344
Week 52 (Day 365 \pm 7)	> 344

DSQ total score will be calculated every 2 weeks (week 0, 2, 4, 6, 8, 10, etc.) based on the scheduled study day starting on Day 1 For example, DSQ total score for Week 2, 4 and 6 will be calculated on Day 15, 29 and 43, respectively. .

For ECGs, OCT, and PFT.

Scheduled Study Visit (Protocol Scheduled Day)	Analysis Visit Window (Study Day)
Baseline (Double-Blind Treatment Period)	≤ 1
Week 0 (Day 1)	1
Week 24 (Day 169 ± 5)	71 to 267
Week 52 (Day 365 ± 7)	> 267

Windowing will be applied prior to any missing data calculations. The measurement that meets the Baseline criteria described in Section 6.2 will be labeled as “Baseline”. Unscheduled or Screening visits that occurred before the Baseline visit will not be assigned an analysis visit. The early discontinuation visit will be eligible for allocation to an analysis visit. The 2- and 4-Week Follow-Up visits will not be included in the visit windows and will be summarized separately without any window applied.

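### The SAP window for Week 24 lung function and OCT has no cut at the first extension dose, so a placebo subject's test on etrasimod can be tabulated as a double-blind Week 24 value

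*Protocol*

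**What the plan says.** **Timing of the tests.** In the Protocol, Appendix 1, Table 7, footnote i states: "Post-screening PFTs may be performed within 7 days of the study visit". Footnote j states: "Scheduled non-screening ophthalmoscopy with OCT may be performed within 7 days of the study visit". Neither footnote requires the test to come before dosing. The same table's footnotes do place ECG, laboratory and PK samples relative to the dose.

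**Timing of the switch.** Protocol 9.4.1 sets the order on the day: "At the Week 24 visit, vital signs should be measured first, followed by ECG, predose PK sample collection, study drug dosing at the study site". PFT and OCT are not in that sequence. Table 7 footnote a says the Week 24 visit "may also serve as the Day 1 visit of the Extension Treatment Period". Under Protocol 6.4, placebo subjects are re-randomized to etrasimod 1 mg or 2 mg for the extension, while subjects already on etrasimod keep their dose.

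**Assignment to visits.** SAP 6.4 has a separate block of windows, headed "For ECGs, OCT, and PFT". Its Week 24 window is Study Day 71 to 267, and everything after Day 267 is Week 52. Study Day counts from the first dose of the study. If several results fall in one window, the nearest to the scheduled day is used, with ties going to the earlier. SAP 6.3 makes retests, unscheduled tests and early termination tests eligible, and lets every measurement count in abnormality and worst-case summaries.

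**Extension baseline.** SAP 6.2 states: "Baseline for the Extension Treatment Period is defined as the last non-missing measurement taken prior to the date of first dose in Extension Treatment Period".

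**The concern.** Set together, these rules let a placebo subject be dosed with etrasimod at the Week 24 visit, have the PFT or OCT some days later, and see the result tabulated under placebo at Week 24. The error is one-sided. Subjects in the etrasimod arms stay on the same dose, so only the placebo reference changes drug. Any early effect of the drug on lung function or the macula would move the placebo column towards the active columns and narrow the contrast.

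The placebo arm is small, and selecting a dose on efficacy and safety is a primary objective, so the descriptive safety tables will be read closely. The same late test also cannot serve as the extension baseline, because that baseline must precede the first extension dose.

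**Working it through.** **1. The plan's window, reproduced.** Week 24 is Day 169 and Week 52 is Day 365 (SAP 6.4). Half the distance is (365 − 169) / 2 = 98 days. Then 169 + 98 = 267 and 169 − 98 = 71, the stated limits. The upper limit is thus the midpoint to Week 52. It takes no account of the change of treatment at Week 24.

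**2. Where the scheduled test can fall.** The Week 24 visit is Day 169 ± 5, so Days 164 to 174. Adding 7 days on either side gives Days 157 to 181, all inside 71 to 267. If the first extension dose is given at the visit, the latest permitted test comes 7 days after it.

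**3. How long the window stays open after the switch.**
- Dose on Day 164: 267 − 164 = 103 days (14.7 weeks)
- Dose on Day 169: 267 − 169 = 98 days (14.0 weeks)
- Dose on Day 174: 267 − 174 = 93 days (13.3 weeks)

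**4. What the selection rule does.** The last column admits only tests before the first extension dose.

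| First extension dose | Test days | Distance from Day 169 | Chosen by SAP 6.4 | Chosen with a cut at the dose |
|---|---|---|---|---|
| Day 164 | 162 and 171 | 7 and 2 | 171, on etrasimod | 162 |
| Day 164 | 160 and 170 | 9 and 1 | 170, on etrasimod | 160 |
| Day 169 | 176 only | 7 | 176, on etrasimod | missing |

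The first two rows show that a valid predose test can be displaced by a later one. Table 7 footnote i asks for a repeat PFT after an abnormal Week 24 result, so such pairs can arise.

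**5. Routes to values later in the window.** The extension schedules no PFT or OCT before Week 52 other than at early termination or follow-up (Table 8), and SAP 6.4 keeps follow-up visits out of the windows. That leaves:
- the repeat PFT in footnote i;
- unscheduled tests for respiratory or visual symptoms (Protocol 10.6.5 and 10.6.7.6);
- early termination during the extension (Table 8);
- delays under Appendix 11.

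**6. Size.** Planned placebo subjects: 96 × 2/8 = 24. One changed classification: 1/24 = 4.2 percentage points. A test that leaves the subject's classification unchanged moves the incidence by nothing.

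**7. Age of a fallback baseline.** Table 7 schedules PFT and OCT at Screening and then not until Week 24 or early termination. From Day 1 to Day 169 is 168 days, or 24 weeks. With Screening up to 35 days earlier, 168 + 35 = 203 days, or 29 weeks. If the only Week 24 test is post-dose, the extension baseline would therefore normally be about 24 to 29 weeks old.

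**The case against.** The best defence is SAP 18, which says that safety is analysed for each period in turn, and SAP 5.7, which derives a Safety Set for each period and analyses the extension by treatment sequence. A programmer could read these as a split at the first extension dose. They show intent, and misreporting is not what the plan sets out to do. But no date rule is given for PFT or OCT, whereas SAP 18.1 does give one for adverse events. The explicit window in 6.4 points the other way. Timing of the analysis does not help: SAP 4.1 runs the Main Analysis once every subject has reached Week 24 or left, when early enrollees may already have extension results.

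Several stronger readings are tempting, and the documents do not support them:

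- **That the placebo rates of adverse events of special interest are contaminated.** Those tables count treatment-emergent events. SAP 18.1 starts extension events at the first extension dose, and SAP 18.2.6 limits the placebo exposure-adjusted rate to the double-blind period.
- **That placebo values may typically reflect 14 weeks of etrasimod.** The scheduled test carries at most about 7 days. It may also be done before the visit, and Table 7 footnote q allows bridging treatment, so a test after the visit can still precede the switch.
- **That every post-dose test shifts an incidence by 4.2 points.** It must also change the subject's classification. SAP 18.8.2 sets markedly abnormal FEV₁ or FVC below 50% predicted, while entry excluded a confirmed value below 70%, so a change should be uncommon. The figure does not apply to central foveal thickness, which is summarized as a value and a change.
- **That extension change is always measured from a stale baseline.** This happens only when no later predose test exists. Protocol 11.9 also reports change from the double-blind baseline.

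**Conclusion.** The point stands as a gap in the analysis rules. Followed literally, SAP 6.4 can place a placebo subject's on-etrasimod PFT or OCT in the double-blind Week 24 column of the descriptive by-visit tables, and SAP 6.3 can bring it into the abnormality and worst-case summaries. Two programmers could produce different placebo columns from the same data.

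The reach is limited. No efficacy result and no table based on treatment-emergent events is touched, and SAP 18 plans no statistical comparison of safety data unless otherwise specified. The scheduled Week 24 ECG shares the window but is ordered before dosing.

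The number of subjects affected cannot be derived from the documents. The 4.2 points assume that all 24 planned placebo subjects are in the denominator; if fewer are tested, one changed classification weighs more. The 7-day figure assumes that the first extension dose is given at the Week 24 visit.

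**What to change.** In SAP 6.4, for PFT and OCT:

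1. End the double-blind Week 24 window at the first extension dose, so that only earlier assessments qualify. Apply the same cut to the double-blind abnormality and worst-case summaries. For subjects who do not enter the extension, keep the current window.
2. Assign assessments after that dose and up to Day 267 to a separately labelled extension post-baseline window. Without this step they would have no visit label, because Week 52 begins only after Day 267.
3. Flag subjects whose extension baseline is the Screening value.

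Tie the cut to each subject's actual first extension dose, so that a test done on bridging treatment stays in the double-blind period.

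The cost is one dated rule, one extra window and one flag. A few double-blind Week 24 PFT or OCT values will become missing. Neither the timing of the tests nor the site-facing schedule needs to change.

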APPENDIX 2: EOSINOPHILIC ESOPHAGITIS HISTOLOGY SCORING SYSTEM

Table 9: Eosinophilic Esophagitis Histology Scoring System Definitions

Each feature will be scored separately for grade (severity) or stage (extent) of abnormality using a 4-point scale (0 = normal; 3 = most severe or extensive).

Features	Definition
Eosinophilic inflammation	Based on peak eosinophil count
Basal zone hyperplasia	Basal zone occupies more than 15% of total epithelial thickness
Eosinophil abscess	Eosinophil aggregate that disrupts the underlying epithelial architecture
Eosinophil surface layering	Eosinophils align in one or more rows in the upper third of the epithelium
Dilated intercellular spaces	Intercellular bridges are visible in paracellular spaces
Surface epithelial alteration	Surface epithelial cells stain more darkly than normal and eosinophils that may be present among the altered epithelial cells
Dyskeratotic epithelial cells	Epithelial cells with deeply staining cytoplasm and shrunken hyperchromatic nuclei that generally occur singly and may be found anywhere in the epithelium
Lamina propria fibrosis	Coalesced fibrils form fibers of varying diameter

Source: [67].

APPENDIX 3: EOSINOPHILIC ESOPHAGITIS ENDOSCOPIC REFERENCE SCORE

Major features

- Fixed rings (also referred to as concentric rings, corrugated esophagus, corrugated rings, ringed esophagus, trachealisation)
 - Grade 0: none
 - Grade 1: mild (subtle circumferential ridges)
 - Grade 2: moderate (distinct rings that do not impair passage of a standard diagnostic adult endoscope (outer diameter 8-9.5 mm))
 - Grade 3: severe (distinct rings that do not permit passage of a diagnostic endoscope)
- Exudates (also referred to as white spots, plaques)
 - Grade 0: none
 - Grade 1: mild (lesions involving < 10% of the esophageal surface area)
 - Grade 2: severe (lesions involving > 10% of the esophageal surface area)
- Furrows (also referred to as vertical lines, longitudinal furrows)
 - Grade 0: absent
 - Grade 1: present
- Edema (also referred to as decreased vascular markings, mucosal pallor)
 - Grade 0: absent (distinct vascularity present)
 - Grade 1: loss of clarity or absence of vascular markings
- Stricture
 - Grade 0: absent
 - Grade 1: present

Minor features

- Crepe paper esophagus (mucosal fragility or laceration upon passage of diagnostic endoscope but not after esophageal dilation)
 - Grade 0: absent
 - Grade 1: present

Source: [52].

APPENDIX 4: DYSPHAGIA SYMPTOM QUESTIONNAIRE

1. Since you woke up this morning, did you eat solid food?

Possible responses:

- *Yes*
- *No*

2. Since you woke up this morning, has food gone down slowly or been stuck in your throat?

Possible responses:

- *Yes (2)*
- *No (0)*

3. For the most difficult time you had while swallowing food today, did you have to do anything to make the food go down or to get relief?

Possible responses:

- *No, it got better or cleared up on its own (0)*
- *Yes, I had to drink liquid to get relief (1)*
- *Yes, I had to cough and/or gag to get relief (2)*
- *Yes, I had to vomit to get relief (3)*
- *Yes, I had to seek medical attention to get relief (4)*

4. The following question concerns the amount of pain you have experienced when swallowing food. What was the worst pain you had while swallowing food today?

Possible responses:

- *None, I had no pain (0)*
- *Mild (1)*
- *Moderate (2)*
- *Severe (3)*
- *Very Severe (4)*

The Dysphagia Symptom Questionnaire questions above will be administered via the electronic diary (eDiary), which will be completed daily in the evening after subjects have their last meal of the day.

APPENDIX 5: FOOD AVOIDANCE QUESTION

If you did not try to eat solid food today, what is the primary reason for this?	
Mark  in applicable box(es).	
	Not applicable because I ate solid food today
	Because of eosinophilic esophagitis symptoms
	Because of other reasons

The Food Avoidance Question will be administered via the electronic diary (eDiary), after subject completes the Dysphagia Symptom Questionnaire diary questions.

APPENDIX 6: PATIENT GLOBAL IMPRESSION OF SEVERITY

Please choose the response below that best describes the severity of your eosinophilic esophagitis symptoms over the past 7 days.	
Mark  in one box below.	
	None
	Mild
	Moderate
	Severe

APPENDIX 7: PATIENT GLOBAL IMPRESSION OF CHANGE

Please choose the response below that best describes the overall change in your eosinophilic esophagitis symptoms since you started taking the study medication.
 
Mark  in one box below.
	
	Much better
	A little better
	No change
	A little worse
	Much worse

If you had a change, was it meaningful to you?  Yes  No
	

APPENDIX 8: GRADING OF CLINICAL AND LABORATORY ADVERSE EVENTS

All clinical and clinically significant laboratory abnormalities will be graded according to the Common Terminology Criteria for Adverse Events (CTCAE) Scale for Severity of Adverse Events and Laboratory Abnormalities.

Examples of CTCAE terms and grading are provided for clinical adverse events in [Table 10](#) and for laboratory abnormalities in [Table 11](#).

Table 10: Example of CTCAE Terms and Grading for Clinical Adverse Events

Respiratory, thoracic and mediastinal disorders					
CTCAE Term	Grade 1	Grade 2	Grade 3	Grade 4	Grade 5
Cough	Mild symptoms; nonprescription intervention indicated	Moderate symptoms; medical intervention indicated; limiting instrumental ADL	Severe symptoms; limiting self-care ADL	–	–
Definition: A disorder characterized by sudden, often repetitive, spasmodic contraction of the thoracic cavity, resulting in violent release of air from the lungs and usually accompanied by a distinctive sound.					
Dyspnea	Shortness of breath with moderate exertion	Shortness of breath with minimal exertion; limiting instrumental ADL	Shortness of breath at rest; limiting self-care ADL	Life-threatening consequences; urgent intervention indicated	Death
Definition: A disorder characterized by an uncomfortable sensation of difficulty breathing.					
Wheezing	Detectable airway noise with minimal symptoms	Moderate symptoms; medical intervention indicated; limiting instrumental ADL	Severe respiratory symptoms limiting self-care ADL; oxygen therapy or hospitalization indicated	Life-threatening consequences; urgent intervention indicated	Death
Definition: A disorder characterized by a high-pitched, whistling sound during breathing. It results from the narrowing or obstruction of the respiratory airways.					
Dizziness	Mild unsteadiness or sensation of movement	Moderate unsteadiness or sensation of movement; limiting instrumental ADL	Severe unsteadiness or sensation of movement; limiting self-care ADL	–	–
Definition: A disorder characterized by a disturbing sensation of lightheadedness, unsteadiness, giddiness, spinning or rocking.					
Blurred vision	Intervention not indicated	Symptomatic; moderate decrease in visual acuity (best corrected visual acuity 20/40 and better or 3 lines or less decreased vision from known baseline); limiting instrumental ADL	Symptomatic with marked decrease in visual acuity (best corrected visual acuity worse than 20/40 or more than 3 lines of decreased vision from known baseline, up to 20/200); limiting self-care ADL	Best corrected visual acuity of 20/200 or worse in the affected eye	–
Definition: A disorder characterized by visual perception of unclear or fuzzy images.					
Blood and lymphatic system disorders					
Anemia	Hgb < LLN–10.0 g/dL; < LLN-6.2 mmol/L; < LLN-100 g/L	Hgb < 10.0-8.0 g/dL; < 6.2-4.9 mmol/L; < 100-80 g/L	Hgb < 8.0 g/dL; < 4.9 mmol/L; < 80 g/L; transfusion indicated	Life-threatening consequences; urgent intervention indicated	–
Definition: A disorder characterized by a reduction in the amount of hemoglobin in 100 ml of blood. Signs and symptoms of anemia may include pallor of the skin and mucous membranes, shortness of breath, palpitations of the heart, soft systolic murmurs, lethargy, and fatigability.					

ADL, activities of daily living; CTCAE, Common Terminology Criteria for Adverse Events; Hgb, hemoglobin

Table 11: Example of CTCAE Terms and Grading for Laboratory Abnormalities and Pulmonary Functions Tests

CTCAE Term	Investigations				
	Grade 1	Grade 2	Grade 3	Grade 4	Grade 5
Alanine aminotransferase increased	> ULN-3.0 × ULN if baseline was normal; 1.5-3.0 × baseline if baseline was abnormal	> 3.0-5.0 × ULN if baseline was normal; > 3.0-5.0 × baseline if baseline was abnormal	> 5.0-20.0 × ULN if baseline was normal; > 5.0-20.0 × baseline if baseline was abnormal	> 20.0 × ULN if baseline was normal; > 20.0 × baseline if baseline was abnormal	–

Definition: A finding based on laboratory test results that indicate an increase in the level of alanine aminotransferase (ALT or SGPT) in the blood specimen.
 
Navigational Note: Also consider Hepatobiliary disorders: Hepatic failure
					
Aspartate aminotransferase increased	> ULN-3.0 × ULN if baseline was normal; 1.5-3.0 × baseline if baseline was abnormal	> 3.0-5.0 × ULN if baseline was normal; > 3.0-5.0 × baseline if baseline was abnormal	> 5.0-20.0 × ULN if baseline was normal; > 5.0-20.0 × baseline if baseline was abnormal	> 20.0 × ULN if baseline was normal; > 20.0 × baseline if baseline was abnormal	–

Definition: A finding based on laboratory test results that indicate an increase in the level of aspartate aminotransferase (AST or SGOT) in a blood specimen.
 
Navigational Note: Also consider Hepatobiliary disorders: Hepatic failure
					
Platelet count decreased	< LLN-75,000/mm ³ ; < LLN-75.0 × 10 ⁹ /L	< 75,000 – 50,000/mm ³ ; < 75.0-50.0 × 10 ⁹ /L	< 50,000-25,000/mm ³ ; < 50.0-25.0 × 10 ⁹ /L	< 25,000/mm ³ ; < 25.0 × 10 ⁹ /L	–

Definition: A finding based on laboratory test results that indicate a decrease in number of platelets in a blood specimen.
					
Forced expiratory volume decreased	FEV ₁ % (percentages of observed FEV ₁ and FVC related to their respective predicted values) 99-70% predicted	FEV ₁ 60%-69%	50%-59%	≤ 49%	–

Definition: A finding based on test results that indicate a relative decrease in the fraction of the forced vital capacity that is exhaled in a specific number of seconds.
 
Navigational Note: Also consider Respiratory, thoracic and mediastinal disorders: Respiratory failure or Dyspnea
					
Vital capacity abnormal	90%-75% of predicted value	< 75%-50% of predicted value; limiting instrumental ADL	< 50% of predicted value; limiting self-care ADL	–	–

Definition: A finding based on pulmonary function test results that indicate an abnormal vital capacity (amount of exhaled after a maximum inhalation) when compared to the predicted value.
 
Navigational Note: Also consider Investigations: Forced Expiratory Volume; Respiratory, thoracic and mediastinal disorders: Respiratory failure or Dyspnea
					
Carbon monoxide diffusing capacity decreased	3-5 units below LLN; for follow-up, a decrease of 3-5 units (mL/min/mm Hg) below the baseline value; asymptomatic and intervention not indicated	6-8 units below LLN; for follow-up, an asymptomatic decrease of > 5-8 units (mL/min/mm Hg) below the baseline value; symptomatic and intervention not indicated	Asymptomatic decrease of > 8 units drop; > 5 units drop along with the presence of pulmonary symptoms (eg, > Grade 2 hypoxia or > Grade 2 dyspnea); intervention indicated	–	–

ADL, activities of daily living; ALT, Alanine aminotransferase; AST, Aspartate aminotransferase; FEV₁, forced expiratory volume at 1 second; FVC, forced vital capacity; LLN, lower limit of normal; SGOT, serum glutamic-oxaloacetic transaminase; SGPT, serum glutamic-pyruvic transaminase; ULN, upper limit of normal

